The primary objective of this study is to collect and compare clinical outcomes and surgical data using the commercially available ROSA Knee System instrumentation and conventional instrumentation.

This will be done by analysis of validated outcome measurement tools, radiographs and adverse event data.

The assessments will include:

1. Comparison of planned operative vs. actual operative component position
2. Operative workflow efficiency
3. Patient safety based on incidence and frequency of adverse events.
4. Clinical performance measured by overall pain and function, quality of life data, and radiographic parameters.

VI. Study Design

This is a prospective, multicenter clinical study designed to facilitate the collection and evaluation of workflow efficiency, patient pain and function, and adverse event data. This clinical study will include Persona, NexGen, and Vanguard product families using the ROSA Knee System or conventional instrumentation. The primary objective of this study is to collect and compare clinical and surgical data using the commercially available ROSA Knee System instrumentation and conventional instrumentation.

A maximum of 300 subjects are to be competitively enrolled in this study across all sites; a maximum of 10 U.S sites will contribute, with participating sites each enrolling up to 75 implanted knees. Sites will enroll up to 45 patients using The ROSA Knee System and up to 30 patients using Conventional instrumentation; total study enrollment into these arms are not to exceed 180 subjects and 120 subjects respectively. Once the maximum study enrollment has been reached, enrollment at all sites will be closed.

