4. Patient is willing and able to provide written Informed Consent by signing and dating the IRB or EC approved Informed Consent form
5. Patient is willing and able to complete scheduled study procedures and follow-up evaluations

b. Exclusion Criteria

1. Patient is currently participating in any other surgical intervention studies or pain management studies
2. Patient has undergone contralateral UKA or TKA within the last 18 months
3. Hip pathology with significant bone loss (e.g. avascular necrosis of the femoral head with collapse, severe dysplasia of the femoral head or the acetabulum)
4. Hip pathology severely limiting range of motion (e.g. arthrodesis, severe contractures, chronic severe dislocation)
5. Patient is pregnant or considered a member of a protected population (e.g., prisoner, mentally incompetent, etc.)
6. Patient has previously received partial or total knee arthroplasty for the ipsilateral knee

Note: During the surgical preparation, if there is presence of strong infrared sources or infrared reflectors in the vicinity of the NavitrackERs, the subject cannot continue with the study. A Study Completion form must be completed.

Note: The use of Tibial/Fibular Augments and stems, constrained liners, and any use of guidance systems are excluded from this study

VIII. Study Device Information

The ROSA Knee System and all TKA device components included in this study are commercially available (FDA cleared) products. All implantable device components are intended for long-term survivorship in accordance with product labeling. Please refer to the package insert for additional instructions, information, and indications for use. The ROSA Knee System is intended to assist the

surgeon in providing software-defined spatial boundaries for orientation and reference information to anatomical structures during surgery. The ROSA Knee System application will support the following Zimmer Biomet total knee systems in both cement and cementless options:

a. Persona[®] The Personalized Knee

Persona knee components included in this study are fixed bearing configurations with various component sizes to accommodate anatomical variation. Femoral components replicate native A/P with 21 distinct profiles in 2mm increments.

b. NexGen[®] Complete Knee Solution

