- Complete header information consistently across all source documents for each individual study subject (when study-specific forms are used).
- Be sure that data on the source documents match that which is entered through the electronic data capture (EDC) system

- Use the study subject's unique Case ID number assigned as instructed. Do not provide information that is not requested on the source document.
- Ensure that all fields are completed. For fields completed by the subject, efforts should be made to obtain any missing responses prior to the subject completing their visit.

Pre-operative planning and final post-operative component positioning data will be extracted from The ROSA Knee System at the discretion of the sponsor. This data will be uploaded by the sponsor into the electronic data capture (EDC) system.

2. Data Submission

Completed source documents will be submitted directly to the Sponsor by electronic data capture and submission via a method approved by the Sponsor. Every effort must be made to ensure data submission to the Sponsor is made within 14 days of the visit completion.

3. Quality Assurance of Data

The Investigator should ensure the accuracy, completeness, legibility, and timeliness of the data reported to the Sponsor in the source documents and in all required reports. Data reported on the source documents and clinic records should be consistent, or the discrepancies should be explained. All electronic systems used to create, modify, maintain, or transmit electronic study records will be validated according to 21 CFR Part 11(ii). The Sponsor will maintain quality control systems, in accordance with the Sponsor's policies and procedures.

C. **Reporting Requirements**

1. Investigator Reporting Responsibilities

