Serious Adverse Events and Serious Adverse Device Effects have to be **reported to the Sponsor as soon as possible**. The incidence has to be documented on the Adverse Event Report form over the whole time of the investigation including information on the date of onset, treatment and resolution, as well as assessment of both the seriousness and the relationship to the study device based on the evaluation of the investigator. The outcome of such complications has to be documented and any changes in outcome have to be updated during the course of the study. In case of early termination of the study, further follow-up of the study subject shall proceed according to the hospital's standard procedure.

Device Deficiencies that did not lead to an adverse event but **could have led** to a medical occurrence if suitable actions had not been taken, if intervention had not been made or if circumstances had been less fortunate shall be **reported to the Sponsor as soon as possible**, as well.

The **Investigator** is responsible for reporting all SAEs, SADEs and Device Deficiencies that could have led to a SADE to the **Ethics Committee** if required by **national regulations** or by the Ethics Committee.

See Section X, Subsection E of this protocol for additional information regarding adverse event classifications. All medical events, regardless of classification, are required to be reported on the **Adverse Event Report** form. The Investigator or Designee will also promptly provide the Sponsor with any additional requested information required for the Sponsor to comply with regulatory requirements.

3. Revision

In the event that removal of one or more of the study knee components is necessary, the Investigator will determine the best treatment and/or revision method for the subject.

Prior to revision surgery, the Investigator or qualified Designee must document any significant radiographic findings related to the need for revision on the **Physician Assessment of Post-Op Radiographs** form. An **Adverse Event Report** form must be completed for those findings indicated by an asterisk on the **Physicians Assessment of**

Post-Op Radiograph form.

Once the revision surgery has been completed, the Investigator or qualified Designee must complete an **Adverse Event Report** form as well as a ***Study Completion** form terminating the subject from the study. For the study completion status, select “Study Prosthesis Removed”.

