Note 1: This definition includes events related to the investigational medical device or the comparator.

Note 2: This definition includes events related to the procedures involved.

Note 3: For users or other persons, this definition is restricted to events related to investigational medical devices.

Serious Adverse Event (SAE)⁽ⁱ⁾:

A Serious Adverse Event is any adverse event that

- a. led to death
- b. led to serious deterioration in the health of the subject, that either resulted in:
 1. a life-threatening illness or injury, or
 2. a permanent impairment of a body structure or a body function, or
 3. in-patient or prolonged hospitalization, or
 4. medical or surgical intervention to prevent life-threatening illness or injury or permanent impairment to a body structure or a body function
- c. led to fetal distress, fetal death or a congenital abnormality or birth defect.

Note: Planned hospitalization for a pre-existing condition, or a procedure required by the protocol, without serious deterioration in health, is not considered a serious adverse event.

Adverse Device Effect (ADE)⁽ⁱ⁾:

An Adverse Device Effect is an adverse event related to the use of a medical device.

Note 1: This definition includes adverse events resulting from insufficient or inadequate instructions for use, deployment, implantation, installation, or operation, or any malfunction of the medical device.

Note 2: This definition includes any event resulting from use error or from intentional misuse of the medical device.

Serious Adverse Device Effect (SADE)⁽ⁱ⁾:

A Serious Adverse Device Effect is an adverse device effect that has resulted in any of the consequences characteristic of a serious adverse event.

Device Deficiency⁽ⁱ⁾:

A Device Deficiency is defined as an inadequacy of a medical device with respect to its identity, quality, durability, reliability, safety or performance.

NOTE: Device Deficiencies include malfunctions, use errors, and inadequate labelling.

Device Deficiencies that did not lead to an adverse event but could have led to a medical occurrence if suitable actions had not been taken, if intervention had not been made, or if circumstances had been less fortunate, shall be reported to the Sponsor as soon as possible, as well.

The Sponsor is responsible for determining the final classification of adverse events.

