Performance of the commercially available ROSA Knee System will be evaluated for pain, function, quality of life, and operative efficiency. Data collected in this study will be summarized descriptively and descriptive summaries will be the basis of any study reports issued. These summaries may be used for interim study reports and may also be used to support regulatory submissions, presentations, and/or publications. Additional surgical technique and instrumentation data may be collected and evaluated.

A. General Statistical Methods

Statistical methodology will consist of summarizing collected data descriptively. Categorical data (e.g., gender or race) will be summarized using counts and percentages, and 95% Confidence Interval (CI), over the time periods of interest. Continuous data, such as age, will be summarized by using means, medians, standard deviation, minimum, maximum, and 95% CI over the time periods of interest. Implant survival and return to function will be summarized using a Kaplan-Meier method and presented with rates (as percentages) and confidence intervals. Routine summaries of complication data is represented by frequencies and percentages. Subgroup analysis per indication will also be performed.

B. Sample Size

This study does not have a set of hypotheses to prove and will openly enroll patients to monitor and analyze safety and efficacy. Sample size is capped by a maximum enrollment ceiling per site.

XIII. References

2. No authors listed (2017) Australian Orthopaedic Association National Joint Replacement Registry, Annual Report
3. No authors listed (2017) National Joint Registry for England, Wales and Northern Ireland. 14th Annual Report
4. van der List JP, Chawla H, Joskowicz L, Pearle AD (2016) Current state of computer navigation and robotics in unicompartmental and total knee arthroplasty: a systematic review with meta-analysis. *Knee surgery, sports traumatology, arthroscopy : official journal of the ESSKA* 24 (11):3482-3495

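### The investigator rates seriousness and device relation but the unmasked sponsor sets the final class, and the plan does not say whose rating the by-arm safety summaries use

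*Combined protocol and SAP*

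**What the plan says.** Section X.D.2 has adverse events recorded on the Adverse Event Report form. For serious events it specifies the source of the judgement: "as well as assessment of both the seriousness and the relationship to the study device based on the evaluation of the investigator". Section X.E.1 defines adverse event, serious adverse event, adverse device effect, serious adverse device effect and device deficiency, and closes that list with "The Sponsor is responsible for determining the final classification of adverse events".

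Section V names as one of four assessments in the comparison of robotic with conventional technique: "Patient safety based on incidence and frequency of adverse events". The analysis text in Section XII.A is one sentence: "Routine summaries of complication data is represented by frequencies and percentages". It names no table by arm, by seriousness or by device relation, and does not say whose rating is used.

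Section XII.B adds: "This study does not have a set of hypotheses to prove and will openly enroll patients to monitor and analyze safety and efficacy". No masking of the sponsor is described. Section X.B.1 says: "Pre-operative planning and final post-operative component positioning data will be extracted from The ROSA Knee System at the discretion of the sponsor", and that the sponsor loads these data into the study database. The only independent review mentioned concerns radiographs, and it is optional (Sections VI and IX.l).

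**The concern.** Two parties hold a judgement on the same event, and the one with the last word knows the technique and has a stake in the result. The sponsor's interest is plain without any claim about who sells what: it runs the robot's post-market study, and Section VIII says "The ROSA Knee System application will support the following Zimmer Biomet total knee systems in both cement and cementless options".

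If the study reports serious events by arm, as a safety comparison normally would, the natural source is the class the protocol calls final. The investigator's rating would then stay on the form without being required in any report. Section XII says the summaries may support regulatory submissions and publications. A favourable robotic result would be open to challenge even if no rating had been changed in a biased way, because the plan gives no means of showing that.

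**Working it through.** The plan has no power calculation, event rate or margin to reproduce. The check is a reading of the text, followed by an illustration of scale.

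**Text, side by side**

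- First rating: the investigator, on the report form (X.D.2).
- Final class: the sponsor (X.E.1), with no criteria, limit, reconciliation step or required record of reasons.
- Sponsor's knowledge of technique: it extracts and uploads the robot data (X.B.1), and the database also holds a planning form used only for conventional cases (III, IX.g).
- Rating to be tabulated: not stated (XII.A).
- Effect on the overall count: moving an event between serious and non-serious leaves the number of adverse events unchanged. X.D.2 also requires every medical event to be reported on the form whatever its class. The count could change only if the final class also decides whether something is an adverse event. X.E leaves room for that, because it opens with a scope limited to the operative knee and then defines an adverse event as any untoward medical occurrence.
- Device relation: Section XI (Minimization of Risk) says the knee implants are not the study device, and the Synopsis names the robot as the test article. Relation to the study device therefore has no clear counterpart in the conventional arm.

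**Scale**

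Inputs: Section VI says "total study enrollment into these arms are not to exceed 180 subjects and 120 subjects respectively" (robotic first). I assume full enrolment and count each subject at most once. The event rates are assumptions, because the documents give none.

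- One event: 1/180 = 0.56 points (robotic); 1/120 = 0.83 points (conventional).
- 95% half-width for the difference: 1.96 × √[p₁(1−p₁)/180 + p₂(1−p₂)/120].

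| Assumed start | Half-width at start | Change | Result | Difference |
|---|---|---|---|---|
| 18/180 vs 12/120 (10% each) | 6.9 points | 4 robotic downgrades | 14/180 = 7.8% vs 10.0% | −2.2 points |
| same | 6.9 | 6 robotic downgrades | 12/180 = 6.7% vs 10.0% | −3.3 |
| 9/180 vs 6/120 (5% each) | 5.0 | 3 robotic downgrades | 6/180 = 3.3% vs 5.0% | −1.7 (ratio 1.00 to 0.67) |
| 11/180 vs 4/120 (6.1% vs 3.3%) | 4.7 | 5 robotic downgrades | 6/180 = 3.3% vs 3.3% | +2.8 to 0 (ratio 1.83 to 1.00) |

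After the four or six downgrades in the 10% case the half-width is 6.6 or 6.5. All these shifts lie inside the interval. They also need a large share of the robotic events to move: 4/18 = 22%, 6/18 = 33%, 3/9 = 33%, 5/11 = 45%.

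Upgrades work as well. From 18/180 vs 12/120, raising two conventional events gives 14/120 = 11.7% and a difference of −1.7 points, the same as three robotic downgrades (15/180 = 8.3% vs 10.0%).

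**The case against.** The strongest reply is that the output at risk is not a planned output. Section XII.A promises frequencies and percentages of complications, and Section V speaks of the incidence and frequency of adverse events. Neither promises serious events by arm. This stands as a limit: the point concerns a table that a safety comparison would naturally contain, and whose source should be fixed before it is made.

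Second, the sentence in X.E.1 is followed directly by the sponsor's duty to report unanticipated serious device effects, so it may be meant only for regulatory categorisation. That is a fair reading, but the text does not confine it to that use, and no other passage names the rating for study tables.

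Third, there are safeguards. The investigator's rating is on the form, source documents must match the database, electronic systems must be validated to 21 CFR Part 11, and the investigator reports serious events to the ethics committee where required. A change may therefore be traceable. What is missing is a rule that both ratings be reported and disagreements shown.

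Fourth, sponsor review can improve consistency across sites, and several seriousness criteria, such as death and hospitalisation, leave little discretion. Both are true, and the fix keeps sponsor review.

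Some stronger readings are tempting. A reader might infer that rates have been or will be shifted; the documents show only that nothing prevents it. A reader might infer that the total adverse event count is exposed; it is not, unless the final class also decides what is an event. A reader might infer that device-related rates by arm are at risk, or that a very few changes could empty that category. The documents give no device-related event rate, and the comparison has no clear meaning in the conventional arm. A reader might also conclude that the sponsor should be barred from lowering a rating. An unmasked sponsor could still raise conventional events only, so a one-way bar does not close the route.

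**Conclusion.** The point holds in a limited form. The protocol bases the first rating on the investigator and gives the final class to an unmasked, interested sponsor, without saying which is reported. Any by-arm summary of serious events would by default rest on the sponsor's class alone.

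The size cannot be fixed from the documents. At the ceilings of 180 and 120, under assumed rates between about 3% and 10%, three to six reclassified robotic events move the difference by 1.7 to 3.3 points. That is within sampling error, but the study is descriptive and tests no hypothesis, so readers will look at the point estimates. With few events a handful of changes can create or remove an apparent difference. It merits a change because the remedy is cheap, not because an error has been shown.

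**What to change.** In X.E.1, state that the investigator's seriousness and relation ratings are kept unchanged in the database beside the sponsor's, and that every change, in either direction, is recorded with its date and reason. State also whether the final classification can decide if something is an adverse event at all.

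In Section XII:

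- Tabulate serious events by arm, with the investigator's rating as the main table.
- Show the sponsor's rating beside it, with a count of events rated serious by either party as a sensitivity summary.
- List all disagreements by arm, with reasons.
- Report relation to the robot for the robotic arm only.

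The cost is one extra field, one table and one listing. Reported serious counts may be slightly higher. Investigators also know the technique, so this reduces the risk of bias without removing it.

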Version 1.0	1 March 2018	Initial Document	[name]
Version 2.0	5 September 2019	Additional CRF added to Section III – Data Collection Overview, and Section IX – Study Procedures	[name]
Version 3.0	14 October 2019	Changes to sections II and VI: -Increase in maximum enrollment per site. -Removal of specific requirements regarding equivalent enrollment into robotic/conventional groups	[name]
Version 3.1	31 Mar 2020	Changes to section II and VI include an increase in maximum number of research sites from 6 to 10; as well as, sites will enroll competitively up to the maximum allowed per site, or until the max study population is achieved. Correction of typographical/grammatical errors throughout document	[name]

II. Study Synopsis

TITLE:	ROSA Total Knee Post Market Study
SPONSOR:	Zimmer Biomet Inc., Warsaw, IN
PROTOCOL NUMBER	CMU2018-34K
STUDY OBJECTIVES	
The primary objective of this study is to collect and compare clinical outcomes data using the commercially available ROSA Knee System and conventional instrumentation.
 
The assessments will include:
 
1. Planned vs actual component positioning.2. Workflow efficiency.3. Patient safety based on incidence and frequency of adverse events.4. Clinical performance measured by overall pain and function, quality of life data, and radiographic parameters.
TARGET POPULATION:	Patients qualifying for primary total knee arthroplasty who meet the inclusion/exclusion criteria for study participation
STUDY DESIGN:	Prospective, multicenter study, using Zimmer Biomet commercially available Persona, Vanguard, and NexGen total knee implant systems.
STUDY TYPE:	Post-market
SAMPLE SIZE:	A Maximum study enrollment of 300 subjects competitively enrolled at up to 10 U.S. sites, with participating sites each enrolling up to 45 Robotic knees and up to 30 conventional knees; with a max site enrollment, of up to 75 total knees. Once the maximum study enrollment has been reached, enrollment at all sites will be closed.

LENGTH OF STUDY:	
One-year Post-operative study; Post-op follow-up visits include: 6 weeks, 3months, and 1 year. Total Enrollment time: 12-18 Months. Total Study Length: 2 - 2.5 years

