Investigators will be skilled in total knee arthroplasty and experienced implanting Persona, NexGen, and/or Vanguard knee systems. Each Principal Investigator will be responsible for obtaining Institutional Review Board (IRB) approval as required prior to conducting the study. In order to avoid potential selection bias, each Investigator will offer study participation to each consecutive eligible patient presenting as a candidate for primary total knee arthroplasty using the aforementioned implants. Eligible candidates who express interest in study participation will be offered Informed Consent. All potential study subjects will be required to participate in the Informed Consent process and will not be considered enrolled in the study until the candidate has signed and dated the IRB approved Informed Consent Form. Study data cannot be collected until the candidate has completed the Informed Consent process and signed and dated the IRB approved Informed Consent Form. All study subjects will undergo preoperative clinical evaluations prior to their Robotic-assisted total knee arthroplasty.

At the Sponsor's discretion, the Sponsor may request copies of radiographs for independent radiologic review. The Sponsor may request one central reviewer for all radiographs independent

of the surgeon and institution.

VII. Study Population

The study population for primary statistical analysis will be comprised of males and females who require primary total knee arthroplasty and satisfy the inclusion/exclusion criteria outlined in this section of the protocol. In order to avoid potential selection bias, each Investigator will offer study participation to each consecutive eligible patient presenting as a candidate for primary total knee arthroplasty using the commercially available (FDA cleared) Persona, Vanguard, and NexGen knee systems. Eligible candidates who express interest in study participation will be offered Informed Consent. The inclusion/exclusion CRF should not be completed until the study-specific consent form has been completed.

a. Inclusion Criteria:

1. Patient is a minimum of 18 years of age
2. Independent of study participation, patient is a candidate for commercially available *Persona, NexGen, or Vanguard* knee components implanted in accordance with product labeling
3. Patient has participated in the study-related Informed Consent Process

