A **Subject Identification/Informed Consent Log** (Appendix C) will be maintained at the site throughout the course of the study. The purpose of the log is to provide documentation that all enrolled study subjects underwent the Informed Consent process, and signed and dated the IRB or EC approved Informed Consent. All candidates who sign and date the approved Informed Consent for the study must be entered in the log. If a subject signs and dates additional Informed Consent(s) after enrollment (e.g., due to a protocol amendment, protocol revisions, etc.), subsequent signings will also be recorded in the log. The **Subject Identification/Informed Consent** will be filed in the site Regulatory Binder for the study. The proposed date of surgery for each subject will be added to the log. The subject will be considered an active study subject after receiving the study device during surgery. In the event that a subject does not receive the study device at the time of surgery, a **Study Completion** form must be submitted and this will be documented as a screen failure.

d. Subject Enrollment

Once the Informed Consent has been signed and dated by the subject, the subject will be considered enrolled in the study. Robotic and conventional patients should be enrolled using a consecutive and concurrent approach. A unique case identification number (Case ID) will be assigned to each participating subject. This unique case ID number will be used throughout the study for identification. Case ID numbers will be assigned consecutively in ascending order per site, with the starting number for a given site defined by the Sponsor. In the event that the subject does not receive the study device at the time of surgery, the subject will be considered a screen failure and documented on a **Study Completion** form (see above). In the occurrence of a screen failure, the surgeon may have the option to enroll an additional patient as long as the subject did not receive the study device.

e. Monitor Log

The **Site Monitoring Visit Log** (Appendix C) will be maintained throughout the course of the study. The log will contain the visit date, monitor name/signature and the purpose of the visit (i.e. site initiation, onsite interim monitoring (as applicable), site close-out, etc.). The site monitoring visit log will be filed in the site Regulatory Binder for the study.

f. Delegation of Authority (Site Signature Log)

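### The primary objective compares ROSA with conventional instrumentation, yet the plan names no between-arm difference, no interval for one and no adjustment, although no stated rule assigns technique

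*Combined protocol and SAP*

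**What the plan says.** The synopsis (Section II) states the objective: "The primary objective of this study is to collect and compare clinical outcomes data using the commercially available ROSA Knee System and conventional instrumentation". Section V repeats it in wider form, "The primary objective of this study is to collect and compare clinical outcomes and surgical data", and lists four assessments. The first two are "Comparison of planned operative vs. actual operative component position" and "Operative workflow efficiency"; the others are adverse events and clinical performance.

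Section VI sets the numbers: "Sites will enroll up to 45 patients using The ROSA Knee System and up to 30 patients using Conventional instrumentation". Across the study the two arms are capped at 180 and 120 subjects. On entry, Section VI says that "each Investigator will offer study participation to each consecutive eligible patient presenting as a candidate for primary total knee arthroplasty", and Section IX.d says "Robotic and conventional patients should be enrolled using a consecutive and concurrent approach". Section XI adds that taking part is not expected to change a subject's medical treatment.

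On analysis, Section XII.A says "Statistical methodology will consist of summarizing collected data descriptively". It then lists counts, percentages, means, medians, SDs and ranges, 95% confidence intervals, and Kaplan-Meier rates. The only split it names is by indication. Section XII.B says there are no hypotheses to prove. The opening of Section XII makes the descriptive summaries the basis of all reports and allows their use in regulatory submissions and publications.

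**The concern.** A stated aim to compare two techniques needs a stated quantity that compares them. Here the objective is comparative, while the analysis section stops at summaries.

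This matters more because the documents describe no randomisation, matching or allocation rule. The remark in Section XI is consistent with technique being chosen as in usual care. If that choice follows patient characteristics, part of any baseline difference carries through to the 1-year result and can be read as an effect of the technique. If technique differs between sites, site differences can do the same. An adjusted contrast devised later, after the data are seen, would carry less weight than one fixed now.

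**Working it through.** **1. The texts side by side.**
- Objective (Sections II and V): compare two techniques.
- Assignment: not stated anywhere. Consecutive offering (Section VI) limits selection into the study. Concurrent enrolment (Section IX.d) limits calendar-time bias. Neither governs who receives which technique.
- Analysis (Section II, Statistical Reporting, and Section XII): one-sample summaries with intervals. There is no difference, no interval for one, no covariate and no site term.

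**2. The plan's own figures.** The caps agree: 180 + 120 = 300 and 45 + 30 = 75. Four sites at their caps fill the study exactly (4 × 45 = 180; 4 × 30 = 120). There is no minimum per arm at a site, so the caps alone would also allow four ROSA-only and four conventional-only sites, within the limit of 10. The documents give no SD, effect size or power, so no sample-size figure can be reproduced.

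**3. Baseline imbalance (illustration).** Assumed: SD of the Oxford Knee Score (OKS) at 1 year, 8.5 points; slope of 1-year score on baseline score, 0.3 to 0.5; full enrolment and no loss.
- SE = 8.5 × √(1/180 + 1/120) = 8.5 × 0.1179 = 1.002.
- Half-width = 1.96 × 1.002 = 1.96 points. In SD units this is 0.231, so an SD of 7 to 10 gives 1.6 to 2.3 points. With an assumed 10% or 20% loss it is 0.243 or 0.258 SD.
- Shift in the raw difference = slope × baseline imbalance:

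| Imbalance (points) | Shift at slope 0.3 | Shift at slope 0.5 | Share of half-width |
|---|---|---|---|
| 0 | 0 | 0 | 0 |
| 1 | 0.3 | 0.5 | 15% to 25% |
| 3 | 0.9 | 1.5 | 46% to 76% |

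**4. Site (illustration).** Assumed intraclass correlation (ICC) 0.01, 0.05 or 0.10. With V0 = 1/180 + 1/120 = 0.01389, the true variance of the raw difference, in units of SD², is ICC × Σ(nR/180 − nC/120)² + (1 − ICC) × V0, summed over sites, where nR and nC are a site's ROSA and conventional counts. The ratio of the true SE to the naive SE is the square root of this over V0:

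| Split (all total 180 and 120) | Σ | SE ratio at ICC 0.01 / 0.05 / 0.10 |
|---|---|---|
| Four sites at 45:30 | 0 | 0.995 / 0.975 / 0.949 |
| Two at 45:15, three at 30:30 | 0.052 | 1.014 / 1.067 / 1.129 |
| Two at 45:30, two ROSA-only (45), two conventional-only (30) | 0.25 | 1.082 / 1.360 / 1.643 |
| Four ROSA-only (45), four conventional-only (30) | 0.50 | 1.162 / 1.658 / 2.121 |

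Site matters little when every site has both arms and becomes material mainly when some have only one.

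**5. Precision after adjustment.** Assume also a baseline SD of 8 and no remaining site variation. Adjusting for baseline and fixed site effects gives half-width = 1.96 × √((8.5² − slope² × 8²)/I), with I = Σ nR × nC/(nR + nC).
- Four sites at 45:30: I = 4 × 18 = 72, half-width 1.88 (slope 0.3) to 1.73 (slope 0.5).
- Only two both-arm sites: I = 36, half-width 2.66 to 2.45.
- No both-arm site: I = 0, so there is no site-adjusted estimate.

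**The case against.** The strongest reply is that this is an openly descriptive post-market study. That stands: with no hypotheses claimed in Section XII.B, the absence of a test or a power calculation is not a defect.

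A reader might infer that the plan pools the two groups or evaluates ROSA alone, because the opening of Section XII names only ROSA and conventional instrumentation is not mentioned in that section. The documents do not support this. Section VI treats the groups as arms with their own ceilings, and Section V says the objective will be met by analysing outcome tools, radiographs and adverse events. By-arm summaries are the natural reading, and writing this into Section XII is a clarification.

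A reader might also infer that no comparison would be possible. That goes too far. Means and rates with intervals, shown by arm, allow a crude comparison. Two separate intervals are still not an interval for the difference, and neither is adjusted.

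The synopsis places the descriptive summaries alongside an evaluation of surgical technique and instrumentation data, and Section XII has a similar sentence. This may cover the operative assessments, so the differing lists of domains in the two places are a side matter. It names no between-arm method.

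Finally, the numbers are all assumed. That is so. The documents do not show that the arms will differ at baseline or that single-arm sites will arise. Section VI describes sites as enrolling both techniques, and Section IX.d asks for concurrent enrolment. Nobody should conclude from the illustration that the result is biased by a known amount.

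**Conclusion.** The point holds as a gap between objective and analysis. The comparative objective has no prespecified between-arm estimate and no handling of confounding, in a study without a stated assignment rule. It should be fixed. Confidence is high for the textual gap and much lower for its numerical importance, which depends on an imbalance, a slope, an SD and a site distribution that the documents do not give. On the assumed values the effect runs from nothing (no imbalance, both arms at every site) to a shift of about three-quarters of the half-width (3-point imbalance, slope 0.5), before any site confounding.

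**What to change.** In Section XII.A:
- State that all summaries, including adverse events, are given by arm.
- Add one prespecified ROSA-minus-conventional difference with a 95% confidence interval for a functional outcome. OKS at 1 year is a natural candidate, since the synopsis names functional outcomes as the endpoint of interest.
- Adjust it for its baseline value, site and a short fixed list of pre-operative factors already collected, for example age, sex, indication and Kellgren-Lawrence grade. Baseline OKS and demographics are scheduled in Section III, the grade is required by the radiographic part of Section IX, and the planned subgroup analysis implies that indication is recorded. The form fields are not shown and should be checked.
- Report baseline balance by arm and the number per arm at each site, and state that unmeasured confounding remains.

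Alternatively, reword the objective as descriptive by group, without comparative inference. That costs one sentence.

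The first route costs some wording and a little more analysis; no new visit or procedure appears to be needed. Its drawback is that single-arm sites contribute nothing to a within-site contrast, so the adjusted interval widens where they occur and cannot be computed if no site has both arms. The adjustment removes measured imbalance only.
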